## LIST OF ABBREVIATIONS

ACCORD	Academic and Clinical Central Office for Research & Development - Joint office for The University of Edinburgh and Lothian Health Board
CI	Chief Investigator
CRF	Case Report Form
GCP	Good Clinical Practice
ICH	International Conference on Harmonisation
PI	Principal Investigator
QA	Quality Assurance
REC	Research Ethics Committee
SOP	Standard Operating Procedure

# 1 INTRODUCTION

## 1.1 BACKGROUND

Upper limb mobility impairments are a common problem for people with neurological conditions. These impairments can have a detrimental effect of individual's lives and can limit access to everyday technology within the home environment. Consequently, environmental control systems (ECS) have been developed to facilitate access to a range of devices in the home including televisions, alarm systems, and telephones. These systems consist of an access method for example a switch or eye gaze, the controller itself which houses the electronics to control various devices and the output devices themselves. Due to the development of tablet based ECS the software that is used for environmental controls can also be used for the purposes of communication.

A previous study has demonstrated that ECS tend to increase independence and increase the ability of individuals to carry out ADL, socialise and increase quality of life (Brandt et al. 2011). There are however concerns over their design and ease of use (Etinger et al. 2018, Myburg et al. 2017). One particular problem is that the majority of communication aid and environmental control systems aimed at high end users require a screen to be mounted in front of the user. The limitations with this are that the user is only able to control their environment or speak when they are in front of the screen and it is difficult to achieve independent access to the device when the user has been driving their wheelchair, or is moving between a wheelchair and another chair/bed.

Smart glasses technology has been developed in the last decade with Google unveiling their first Google Glass edition in 2012 and subsequently companies such as Epson, Microsoft and Sony also releasing devices (Kim and Choi 2021). Smart glasses consist of a pair of glasses which are equipped with a see-through optical display that enables the user to see both their environment and also a virtual display (Lee and Hui 2018). By using smart glasses, displays are accessible to the user in any location in their environment and this could provide an effective solution for increasing the independent use of communicate aids and environmental control systems.

The existing NHS Lothian environmental control service (<https://www.smart.scot.nhs.uk/service/environmental-control/>) has approximately 100 service users. Smart glasses potentially have the benefit of allowing users who would not be able to use environmental controls to access one. There are no significant risks of harm to users identified.

## 1.2 RATIONALE FOR STUDY

The research question for this study is - what are the impact of smart glasses on the usability and satisfaction of operating an ECS or communication aid.

The outcomes from the study could lead to new ECS/communication aids being developed that incorporate smart glasses as a user display. If this is realised then it could lead to a reduction in the barriers to smart glasses by removing the mounting requirement for a screen. It could also improve how users interact with others by removing a visible screen displaying what the user is writing ahead of it being spoken and therefore increasing privacy. There is also a potential cost benefit to NHS services due to the high costs of specialist mounting bracketry.

## 2 STUDY OBJECTIVES

### 2.1 OBJECTIVES

#### 2.1.1 Primary Objective

To explore the impact of smart glasses on the usability and satisfaction of operating ECS and communication aids.

[figure not shown]
### 2.2 ENDPOINTS

#### 2.2.1 Primary Endpoint

Quest 2.0

## 3 STUDY DESIGN

The evaluation is to be conducted by a UK based NHS Rehabilitation Engineering department. Individuals who currently have an ECS or communication aid on long term loan will trial the device and provide feedback. Questionnaires and interviews will evaluate the usability and the satisfaction that smart glasses provide.

The QUEST 2.0 questionnaire will be used to explore the user's satisfaction both with their existing setup and with the use of the smart glasses.

A semi-structured interview will be used to explore the usability of the smart glasses.

At the end of study participants will not be able to keep the smart glasses. The service will review the results from the study to inform future provision.

## **4 STUDY POPULATION**

### **4.1 NUMBER OF PARTICIPANTS**

The participants will be recruited from the population served by NHS Lothian's Environmental Control Service. The number of participants will be determined by how many participants it is possible to recruit within 12 months – it is expected to be <20. The participants will be referred to service as normal and the clinical intervention (supply of an environmental control system) will proceed irrespective of their participation or otherwise in the study. The only difference to the normal service provision and pathway is the application of the baseline and follow up questionnaires.

### **4.2 INCLUSION CRITERIA**

- i. Existing environmental control system user (age 18-80).
- ii. Neurological condition.
- iii. Cognitive ability to answer the questions and to give consent.
- iv. Current environmental control system is compatible with smart glasses display.

### **4.3 EXCLUSION CRITERIA**

- i. Current environmental control system or communication aid is not compatible with smart glasses display.
- ii. Rapidly deteriorating condition

### **4.4 CO-ENROLMENT**

Co-enrolment will not be allowed in any circumstances.

## **5 PARTICIPANT SELECTION AND ENROLMENT**

### **5.1 IDENTIFYING PARTICIPANTS**

Participants will be identified by Clinical Scientists (who are in the patient's direct care team) working in NHS Lothian's Environmental Control Service (ECS) from a database of existing patients. The patient will be contacted by a Clinical Scientist via telephone, to ask if they wish to take part in the study.

### **5.2 CONSENTING PARTICIPANTS**

Informed consent will be collected by a Clinical Scientist at the initial setup in the form of a consent form. The participants will be sent the information sheet at least 1 week in advance of the initial setup appointment.

#### **5.2.1 Withdrawal of Study Participants**

Participants are free to withdraw from the study at any point or a participant can be withdrawn by the Investigator. If withdrawal occurs, the primary reason for withdrawal will be documented in the participant's case report form if possible. The participant will have the option of withdrawal from:

- (i) all aspects of the study but continued use of data collected up to that point. To safeguard rights, the minimum personally-identifiable information possible will be collected.

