## 6 STUDY ASSESSMENTS

### 6.1 STUDY ASSESSMENTS

The participant will be provided with a set of smart glasses as an alternative display for their existing environmental control system. Training will be provided on how to operate the smart glasses. The initial setup and questionnaire will take between 2-3 hours. Further questionnaires will be completed at a second appointment and will take approximately 1 hour to complete.

Assessment	Screening	Baseline	3 weeks following loan of smart glasses
Assessment of Eligibility Criteria			
Written informed consent			
Demographic data, contact details			
Questionnaire			
Interview			

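### Participants whose glasses fail, or who are withdrawn, before the 3-week visit drop out of the satisfaction and usability results without being counted

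*Combined protocol and SAP*

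**What the plan says.** All references are to the combined protocol and SAP.

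- **Question.** Sections 1.2 and 2.1.1 ask what smart glasses do to the usability of, and satisfaction with, environmental control systems and communication aids. The primary endpoint is QUEST 2.0 (2.2.1). Usability is explored by semi-structured interview (3).
- **Setup.** Section 5.2: "Informed consent will be collected by a Clinical Scientist at the initial setup". Section 6.1: "The participant will be provided with a set of smart glasses as an alternative display for their existing environmental control system", and "The initial setup and questionnaire will take between 2-3 hours".
- **Follow-up.** The schedule in 6.1 and the list in 7 place the second QUEST 2.0 and the only interview at the follow-up appointment, 3 weeks after the loan of the glasses. There is no earlier assessment for someone who stops.
- **Withdrawal.** Section 5.2.1 says that "a participant can be withdrawn by the Investigator", with no criteria, and that "the primary reason for withdrawal will be documented in the participant's case report form if possible". The withdrawal option offered to participants keeps the data already collected in use.
- **Analysis.** Section 9.2 takes out incomplete datasets first, then reports the mean, the change in mean and the standard deviation for each outcome measure.
- **Not stated.** No section defines failed setup, technical failure, non-use or early return as an outcome, or asks for counts of participants set up, still using the glasses or withdrawn.

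**The concern.** Glasses that cannot be linked to a person's system, or that are handed back after a few days, are evidence on usability. Under this plan, that evidence reaches the results only if the person also provides 3-week data. Someone who does not has a baseline QUEST 2.0 of the existing setup and nothing on the glasses, and 9.2 then removes even the baseline.

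The people most likely to be missing at 3 weeks are plausibly those for whom the glasses worked least well. The analysed group would then be selected, after exposure, on something close to the outcome. Section 3 says that the service will use the results to inform future provision, so a result that describes only those who carried on could mislead that decision. With fewer than 20 participants expected (4.1), a few such cases matter.

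**Working it through.** The plan states no sample size, failure rate, dropout rate or power, so it has no figure to reproduce. The check first follows the rules for each kind of participant and then illustrates the size.

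**Step 1: what the rules do.**

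| Participant | Baseline QUEST 2.0 | 3-week QUEST 2.0 and interview | After 9.2 |
|---|---|---|---|
| Uses the glasses and attends at 3 weeks | yes | yes | kept |
| Glasses fail or are returned, but attends at 3 weeks and answers | yes | yes | kept |
| Glasses fail or are returned, or participant is withdrawn; no 3-week data | yes | no | removed |

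The third row is the problem. Nothing in the plan directs such a person into the second row, and nothing reports how many are in the third. Because the follow-up is timed from the loan, a person whose glasses could not be set up may have no defined follow-up date. Sections 5.2.1 and 9.2 also pull apart: one keeps data collected before withdrawal in use, the other discards them as incomplete.

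**Step 2: share hidden.** Let N be the number who consent and k the number in the third row because the glasses failed. The share among all consented is k/N; completers show 0/(N − k). Intervals are exact (Clopper-Pearson) 95%; the upper limit for 0 of m is 1 − 0.025^(1/m).

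Assumed inputs, not from the documents: N = 10, 15 or 19 (19 is the largest whole number below 20) and k from 1 to 5.

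| N | k | k/N (95% CI) | Seen among completers (upper limit) |
|---|---|---|---|
| 10 | 3 | 30.0% (6.7 to 65.2) | 0/7 (41.0%) |
| 15 | 3 | 20.0% (4.3 to 48.1) | 0/12 (26.5%) |
| 19 | 3 | 15.8% (3.4 to 39.6) | 0/16 (20.6%) |
| 19 | 1 | 5.3% (0.1 to 26.0) | 0/18 (18.5%) |
| 10 | 5 | 50.0% (18.7 to 81.3) | 0/5 (52.2%) |

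The last two rows are the extremes of the assumed range.

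**Step 3: effect on the planned summary.** Let C be the mean QUEST 2.0 change in completers and F the mean change the others would have reported. The mean over everyone is [(N − k)C + kF]/N, so the completers' mean exceeds it by (k/N)(C − F).

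- N = 19, k = 3: 3/19 × 1 = 0.16 points for an assumed gap of 1 point; 3/19 × 2 = 0.32 for a gap of 2.
- Whole range: 1/19 × 1 = 0.05 to 5/10 × 1 = 0.50 points for a gap of 1; 1/19 × 2 = 0.11 to 5/10 × 2 = 1.00 for a gap of 2.

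Step 3 applies only to people who used the glasses enough to rate them. For a failed setup there may be no rating to recover, and only a count can show what happened.

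**The case against.** The strongest reply is that no rule makes failure of the glasses a reason to leave. A participant whose glasses failed can attend at 3 weeks, complete QUEST 2.0 and describe the failure at interview. This stands, and it limits the point to people without 3-week data. It does not remove the point, because the plan neither asks for that attendance nor counts those who are absent.

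A second reply is that 5.2.1 asks for the reason for withdrawal and retains earlier data. That also stands in part. A reader might infer from the missing criteria that the Investigator may withdraw anyone at will, or might read a motive into who decides. The documents support neither: they are silent on grounds, and a reason is expected where possible. The reason, however, is not required to appear in the results.

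A third reply is that this is a small, exploratory, descriptive study with no planned proportion of users for whom the glasses worked. That is correct. The shares above describe who is missing from the results; they do not correct a success rate that the study intends to report.

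A stronger reading is also tempting: that a failure at setup could be relabelled afterwards as ineligibility under exclusion criterion i ("Current environmental control system or communication aid is not compatible with smart glasses display"). The documents do not support it. That criterion and its inclusion counterpart ("Current environmental control system is compatible with smart glasses display") concern the existing equipment, not whether the person can read or operate the glasses. In the 6.1 schedule, "Assessment of Eligibility Criteria" is ticked at Screening only, and no step re-applies it after consent.

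**Conclusion.** The point holds for withdrawal and missing follow-up. Three provisions act together: Investigator withdrawal without stated criteria (5.2.1), glasses-related outcomes collected only at 3 weeks (6.1, 7), and removal of incomplete datasets (9.2). Followed as written, they leave anyone without 3-week data out of the satisfaction and usability results, including those for whom the glasses failed.

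The direction, towards a more favourable picture, rests on the assumption that people lost after a failure would have rated the glasses lower than completers. The size is unknown. Three cases hidden among an assumed 19 is a fair illustration, and the assumed range runs from 5.3% to 50.0% of participants. The effect on mean change depends equally on an assumed gap. The change is inexpensive and worth making before enrolment, because the counts depend on recording at the time.

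**What to change.** - **Section 5.2.1.** State that withdrawal, by the participant or the Investigator, does not remove a consented participant from the reported denominator. State that failed setup, technical failure, non-use or early return is recorded, with its cause, as a usability outcome. Separate stopping use of the glasses from leaving the study.
- **Sections 6.1 and 7.** At the second appointment already planned, seek QUEST 2.0 and the interview from those who stopped using the glasses and are willing.
- **Section 9.2.** Replace removal of incomplete datasets with reporting of available data, stating the number behind each summary. This also brings 9.2 into line with the continued use of data in 5.2.1. Beside the QUEST 2.0 summary, report the numbers consented, set up, still using the glasses at 3 weeks, and withdrawn (with reasons).

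The 5.2.1 and 9.2 changes need to be made together: with 9.2 unchanged, these participants would still be deleted from the summary. Nothing here proposes when a participant should be withdrawn.

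Cost: a few sentences and one line on the structured form, with no new visits or staff. The downside is that the headline may look less favourable and some counted participants will have no QUEST 2.0 rating of the glasses, so the denominators for the counts and for the scores will differ and must both be shown.

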## 6 STUDY ASSESSMENTS

### 6.1 STUDY ASSESSMENTS

The participant will be provided with a set of smart glasses as an alternative display for their existing environmental control system. Training will be provided on how to operate the smart glasses. The initial setup and questionnaire will take between 2-3 hours. Further questionnaires will be completed at a second appointment and will take approximately 1 hour to complete.

Assessment	Screening	Baseline	3 weeks following loan of smart glasses
Assessment of Eligibility Criteria			
Written informed consent			
Demographic data, contact details			
Questionnaire			
Interview			

### 6.2 LONG TERM FOLLOW UP ASSESSMENTS

The longest follow up will be 3 weeks.

### 6.3 STORAGE AND ANALYSIS OF SAMPLES

N/A

## 7 DATA COLLECTION

All data will be collected by a Clinical Scientist within NHS Lothian's Environmental Control Service.

1. Participant will complete initial questionnaire **QUEST 2.0** (completed in person at initial appointment)
2. Participant will complete follow up questionnaire **QUEST 2.0 and study specific semi-structured interview** (completed in person at follow up appointment)

### 7.1 Source Data Documentation

Source data is defined as all information in original records and certified copies of original records or clinical findings, observations, or other activities in a clinical study necessary for the reconstruction and evaluation of the study. Source data are contained in source documents.

Source documents are original documents, data and records where source data are recorded for the first time.

1. QUEST 2.0
2. Study specific semi-structured interview

## 7.2 Case Report Forms

Data will be collected on a structured form. –

# 8 DATA MANAGEMENT

[figure not shown]
## 8.1 Personal Data

The following personal data will be collected as part of the research:

- Name, ReTIS number (this is 6 digit identifier used by the ReTIS database – the system used for patient management within the SMART Centre for issuing wheelchairs and environmental control systems etc.), Phone number, Home address, health conditions. This information is collected from the ReTIS database record.

Personal data will be stored by the research team on ReTIS (Local data management software) which is password protected. A mapping spreadsheet will be created to map between the ReTIS number and the participant's study specific code. Personal data will be stored for as long as they are a patient of the Environmental Control Service.

## 8.2 Data Information Flow

\* After a fixed period in accordance with the retention of health records requirements.

### **8.3 Data Storage**

The results of the QUEST 2.0 scores will be recorded on handwritten forms. The results from the semi-structured interview will be recorded on a secure NHS approved device.

A study spreadsheet will be created for saving the results of the QUEST 2.0 scores and the semi-structured interview. This will be on secured NHS Lothian network shared drive accessible only to the study investigators. Handwritten forms will be kept locked in cabinet in the lead investigators office – once transcribed they will be destroyed using the confidential waste.

The semi-structured interview data will be transcribed by the lead researcher onto the spreadsheet. After this the recordings will be deleted from the device.

### **8.4 Data Retention**

Personal data will be stored for the duration of the study and for additional time for the study to be written up – this will be 3 years from the end of the study.

### **8.5 Disposal of Data**

Data will be deleted from the shared drive.

Handwritten forms will be destroyed using the confidential waste.

### **8.6 External Transfer of Data**

Data collected or generated by the study (including personal data) will not be transferred to any external individuals or organisations outside of the Sponsoring organisation(s).

### **8.7 Data Controller**

A data controller is an organisation that determines the purposes for which, and the manner in which, any personal data are processed.

The University of Edinburgh and NHS Lothian are joint data controllers along with any other entities involved in delivering the study that may be a data controller in accordance with applicable laws (e.g. the site).

### **8.8 Data Breaches**

Any data breaches will be reported to the University of Edinburgh ([[contact]](mailto:[contact])) and NHS Lothian ([[contact]](mailto:[contact])) Data Protection Officers who will onward report to the relevant authority according to the appropriate timelines if required.

## **9 STATISTICS AND DATA ANALYSIS**

### **9.1 SAMPLE SIZE CALCULATION**

Due to the small number of participants expected, data will be analysed with descriptive methods and therefore no sample size calculations are required.

### **9.2 PROPOSED ANALYSES**

Incomplete datasets will be removed before undertaking the analysis.

The data will be analysed with descriptive methods with a focus on clinical significance.

Correlation analysis will be conducted to determine relationships between the device use and social context and the satisfaction outcome measures.

For all of the outcome measures the following data will be reported: mean, change in mean between intervals and standard deviation.

Statistical tests will be used to analyse the significance of the relationship between variables.

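### Section 9.2 deletes incomplete datasets without defining them or accounting for those removed, which loses usable data and may overstate satisfaction with the glasses

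*Combined protocol and SAP*

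**What the plan says.** The only missing-data rule is one sentence in section 9.2: "Incomplete datasets will be removed before undertaking the analysis". Neither incomplete nor dataset is defined. No section gives a rule for partly completed QUEST 2.0 forms, a planned count or description of those removed, or a sensitivity analysis.

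Other sections bear on how the rule would work:

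- Section 5.2.1 offers withdrawal from "all aspects of the study but continued use of data collected up to that point". The main reason for withdrawal is recorded where possible, but no reporting of reasons is planned. The investigator may also withdraw a participant.
- Section 4.1, on the number of participants: "it is expected to be <20".
- Section 3 uses QUEST 2.0 to measure "satisfaction both with their existing setup and with the use of the smart glasses". Under sections 6.1 and 7, the form is filled in at baseline and again, with the interview, "completed in person at follow up appointment". Section 6.2 adds: "The longest follow up will be 3 weeks".
- Section 9.2 reports "mean, change in mean between intervals and standard deviation" for every outcome, and also plans correlations of device use and social context with satisfaction.

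**The concern.** There is one group and one measurement of satisfaction with the glasses. A participant who does not attend at 3 weeks has no glasses score. If dislike of the glasses is one reason for not attending, the people left in the analysis are more favourable than the people offered the device. A reader of the mean change would not see this, because the plan does not require the number of non-completers or their reasons to be reported. Section 3 says the service will use the results to inform future provision, so how many people stopped, and why, is useful information in itself.

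Two further problems do not depend on the direction of any bias. Because incomplete is undefined, its meaning could be settled after the data have been seen. The rule would also remove data that were properly collected, such as the baseline QUEST of someone who later withdrew, although section 5.2.1 provides for their continued use.

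**Working it through.** The plan has no figure to reproduce. Section 9.1 says "data will be analysed with descriptive methods and therefore no sample size calculations are required", and no dropout rate, QUEST item count, standard deviation or expected change is given. Everything below except the ceiling on N is an assumption.

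**1. Weight of one person.** With N below 20, the largest case is N = 19. Each person removed is 1/19 = 5.3% of the sample. At N = 10 it is 10%.

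**2. Effect of removal on the mean change.** Let m of N people be removed.

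Mean over all N = [(N - m) × mean change in those kept + m × mean change in those removed] / N

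Bias of the reported mean = (m/N) × (mean change in those kept - mean change in those removed)

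Assume N = 19 and a mean change of +0.5 in those kept, so the rule reports +0.50 whatever happened to the others.

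| Removed (m) | Their change 0 | Their change -1 | Their change -2 |
|---|---|---|---|
| 4 | 7.5/19 = +0.39 | (7.5 - 4)/19 = +0.18 | (7.5 - 8)/19 = -0.03 |
| 6 | 6.5/19 = +0.34 | (6.5 - 6)/19 = +0.03 | (6.5 - 12)/19 = -0.29 |

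These are the unfavourable cases. If those removed changed by the same +0.5, the bias is zero. If they did 0.5 point better than those kept, the bias with 4 removed is (4/19) × (-0.5) = -0.11, so the rule would understate the change.

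**3. Blank items, if a single blank counts as incomplete.** With k items per form, two forms and an independent chance q that an item is blank, the expected number kept is 19 × (1 - q)^(2k).

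| Items per form (assumed) | q = 1% | q = 2% |
|---|---|---|
| 8 | 16.2 | 13.8 |
| 12 | 14.9 | 11.7 |

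Blanks of this kind are unrelated to satisfaction, so they do not shift the mean. They cost precision: with the same standard deviation, the standard error rises by a factor of √(19/17) = 1.06 with 17 kept and √(19/13) = 1.21 with 13 kept.

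**4. Sections 5.2.1 and 9.2 side by side.** A withdrawer with a baseline form and no follow-up form is incomplete on any ordinary reading. Section 5.2.1 keeps that person's data in use; section 9.2 removes them before any analysis. What is lost is the baseline score. No analysis rule can supply an observed change for that person, because the glasses score was never collected.

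**The case against.** The strongest reply is that this is a small, exploratory, descriptive study with short follow-up and no hypothesis, and that the worst outcomes can only be reached by reading more into the plan than it says. Much of that stands.

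- A reader might infer that the rule removes everyone who gave up on the glasses. The documents do not support this. Someone who stops using the device can still attend at 3 weeks and score it low. Section 5.2.1 concerns leaving the study, not putting the glasses aside.
- A reader might infer that one blank item deletes a participant. That is one possible reading of an undefined term, not a stated rule. Forms are completed in person with a Clinical Scientist collecting the data, so blanks may be rare.
- A reader might infer that the result is biased towards success. No success criterion exists, exits may be due to illness, burden or an investigator's decision, and random blanks create no upward bias.
- Section 5.2.1 permits continued use of earlier data but does not promise inclusion in every analysis. The conflict with section 9.2 is a tension to be resolved, not a flat contradiction on every reading.

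The reply does not remove the gaps. The deletion rule is unconditional, its key term is undefined, nobody is tasked with reporting who was removed, and the plan does not say that people who stop early will be asked for follow-up data. Being descriptive does not protect a mean and standard deviation from selective loss.

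**Conclusion.** The concern holds in a limited form. As written, section 9.2 discards usable data, leaves the meaning of incomplete open, is in tension with section 5.2.1, and may overstate satisfaction if non-completion is related to dislike of the glasses. Neither the direction nor the size of the bias can be established from the documents.

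Under the assumptions shown, losing 4 of 19 could turn an all-participant mean of between -0.03 and +0.39 into a reported +0.50. That range rests on an assumed number removed, an assumed completer change of +0.5 and assumed changes of 0 to -2 in those removed. In a sample this small, a handful of removals is enough to matter, and that is reason to settle the rule before data are collected.

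**What to change.** Replace the sentence in section 9.2 with:

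> Each analysis uses every participant with data for it. A missing interview or a blank item does not remove the participant's other data. Partly completed QUEST forms are scored by a rule fixed before data are examined. Baseline scores, number and reasons are reported for all participants without follow-up, and the before-after change is also shown over a range of assumed values for them, including no change.

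The documents do not give the QUEST scoring method, so the sponsor should choose the partial-form rule and write it down in advance.

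In sections 6.1 and 7, add that participants who stop using the glasses but have not withdrawn from the study are invited to complete the follow-up QUEST and interview, either when the glasses are returned or at the 3-week appointment. This step matters most, because changing the deletion rule cannot recover data that were never collected. It must not extend to people who have withdrawn from all aspects of the study.

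The cost is a minor protocol amendment through the route in section 13.1, slightly noisier scores from partial forms, and a reported change that may look less favourable. No extra participants are needed.
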